# 13.7 Analysis of Secondary Endpoints

Response rate will be assessed as per RECIST, see Section 9.1. Results will be reported with 95% confidence intervals. All patients will be evaluable for response rate. Progression-Free Survival (PFS) will be defined as the duration of time from start of treatment to time of objective disease progression or death. Overall survival (OS) will be defined as the duration of time from start of treatment until death. Analysis will be performed using the Kaplan-Meier method. All patients will be evaluable for survival endpoints.

A summary of the adverse events, grading according to CTCAE and their attributed relatedness to treatment will be provided as a measure of patient safety and tolerability. All patients will be included in the safety analyses.

The first six patients in the study will constitute a safety cohort as outlined in section 5.1. If >1 patient has a grade 3 or higher treatment-related adverse event during cycle 1 of treatment, the dose will be de-escalated as outlined. Six additional patients will be treated at the lower dose to establish safety prior to proceeding to open enrolment of the remainder of the trial. The probability of stopping at the initial dose in order to dose de-escalate and the probability of stopping the trial after the safety run in at the lower dose based on assumptions about the associated underlying toxicity rates are as follows:

True toxicity rate	Probability of reducing the starting dose	Probability of stopping the trial
0.05	0.265	0.033
0.1	0.468	0.114
0.2	0.738	0.345
0.3	0.883	0.580
0.4	0.954	0.767
0.5	0.985	0.890

Biopsies from pre, post and on-treatment will be obtained to facilitate comparative analysis by next-generation sequencing, single-cell RNA sequencing, transcriptional profiling and an evaluation of the emergent resistance mechanisms at the time of progression. Analyses for these outcomes may include the Cox proportional Hazard models for the examination of the relationship between changes in sequencing parameters and time to progression, Sign-Rank test to compare pre and post measurements of gene expression for genes of interest and other correlation tests such as linear regression to examine relationship between relevant outcomes.

The feasibility of single-cell sorting and transcriptional analysis of on-treatment biopsies will be assessed based on the rate of interpretable results. The lower-bound of the 95% CI will be provided for this rate and will serve as an indication of the ability to use such methods in an expanded setting.

The results of longitudinal ctDNA analysis before, during and after treatment are exploratory and will be evaluated in a descriptive manner.

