# 5. TREATMENT PLAN

## 5.1 Treatment Regimen

All patients will receive combination therapy with EGF816 and gefitinib in an open-label fashion. A treatment cycle will be defined as 28 days. After completing 1 year of study treatment, visits will occur every 6 weeks.

The first six patients enrolled in the study will constitute a safety run-in; if severe unexpected toxicities are observed during cycle 1 among these six patients, further expansion cohorts at lower dose levels will be explored. Severe unexpected toxicities will be defined as any grade 3 or higher adverse event assessed to be treatment-related by the treating physician occurring in > 1/6 patients during the safety run-in. Rash will be excluded as grade 3 rash during the 1st cycle has occured with each drug individually and is typically responsive to dose hold. If >1 patient has a grade 3 or higher treatment-related adverse event during cycle 1 of treatment, we will de-escalate treatment to gefitinib 250 mg QD and EGF816 100 mg QD.

EGF816 will be supplied by Novartis to the investigational drug pharmacy at all participating sites. Gefitinib will be supplied directly to the patient through prescription as a commercial product. As stated in the eligibility criteria, only patients with insurance approval to obtain gefitinib or who agree to self-pay for gefitinib will be able to participate in this study. Upon signing of the study ICF and confirmation of eligibility, participants will be prescribed a 30-day (one 28-day cycle; with two additional pills in case of lost, dropped pills) supply of gefitinib. C1D1 will begin only once the supply of gefitinib is in the patient's possession.

All patients will receive gefitinib 250 mg orally once daily and EGF816 100 mg orally once daily without interruption, unless an interruption is required to manage treatment-related toxicity (as outlined in Tables 6-1 and 6-2). Patients will be monitored at the start of each 28-day treatment cycle. Treatment will be administered on an outpatient basis. The participant will be requested to maintain a medication diary of each dose of medication. The medication diary will be returned to clinic staff at the end of each cycle.

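### The run-in table's probability of reducing the starting dose matches a trigger of at least 1 of 6 patients, but the written rule needs more than 1 of 6, so the column is 9 to 39 points too high

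*Combined protocol and SAP*

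**What the plan says.** The run-in cohort has six patients. Section 13.7 states: "The first six patients in the study will constitute a safety cohort as outlined in section 5.1".

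The trigger appears in two places. Section 5.1 defines severe unexpected toxicity as "any grade 3 or higher adverse event assessed to be treatment-related by the treating physician occurring in > 1/6 patients", leaves rash out of the count, and says that when more than one patient has such an event "during cycle 1 of treatment, we will de-escalate treatment to gefitinib 250 mg QD and EGF816 100 mg QD". Section 13.7 repeats the threshold: "If >1 patient has a grade 3 or higher treatment-related adverse event during cycle 1 of treatment, the dose will be de-escalated as outlined". It adds that six more patients are then treated at the lower dose before general enrolment continues.

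The table in section 13.7 follows. Its introduction describes the first probability column as "The probability of stopping at the initial dose in order to dose de-escalate" and the second as "the probability of stopping the trial after the safety run in at the lower dose". The first column is headed "Probability of reducing the starting dose". The printed values, for true toxicity rates 0.05, 0.1, 0.2, 0.3, 0.4 and 0.5, are:

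- first column: 0.265, 0.468, 0.738, 0.883, 0.954, 0.985
- second column: 0.033, 0.114, 0.345, 0.580, 0.767, 0.890

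**The concern.** The first column looks too high for a rule that tolerates one event in six. At a true rate of 5%, two or more events in six patients should be rare, yet the table has the dose reduced more than a quarter of the time.

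The table gives the only operating characteristics for the run-in, so it is what a reader would use to judge how well the rule protects patients starting an untested two-drug combination. If the column is overstated, the rule appears much more sensitive to a toxic starting dose than it is. It also appears far more likely to reduce a well-tolerated dose without need.

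**Working it through.** **Inputs.** Cohort size n = 6 (sections 5.1 and 13.7). Trigger: more than 1 of 6, that is X ≥ 2 (both sections). True toxicity rates p and printed probabilities: the table in section 13.7. X is binomial with n = 6 and probability p.

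**Formulas.**

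- At least one event: P(X ≥ 1) = 1 − (1 − p)^6
- Exactly one event: P(X = 1) = 6p(1 − p)^5
- Written rule: P(X ≥ 2) = 1 − (1 − p)^6 − 6p(1 − p)^5

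**Example, p = 0.2.** (0.8)^6 = 0.2621 and 6 × 0.2 × (0.8)^5 = 0.3932. So P(X ≥ 1) = 0.7379 and P(X ≥ 2) = 0.7379 − 0.3932 = 0.3446 (from unrounded terms). The printed value is 0.738.

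**All rows.**

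| p | Printed, first column | P(X ≥ 1) | P(X ≥ 2), written rule | Printed minus rule (points) | P(X = 1) |
|---|---|---|---|---|---|
| 0.05 | 0.265 | 0.2649 | 0.0328 | 23.2 | 0.2321 |
| 0.1 | 0.468 | 0.4686 | 0.1143 | 35.4 | 0.3543 |
| 0.2 | 0.738 | 0.7379 | 0.3446 | 39.3 | 0.3932 |
| 0.3 | 0.883 | 0.8824 | 0.5798 | 30.3 | 0.3025 |
| 0.4 | 0.954 | 0.9533 | 0.7667 | 18.7 | 0.1866 |
| 0.5 | 0.985 | 0.9844 | 0.8906 | 9.4 | 0.0938 |

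**Reproducing the printed column.** P(X ≥ 1) matches it in all six rows; the largest difference is 0.0007. Other candidates were tried: at least 2 or 3 of 6, at least 2 of 7 to 12, at least 3 of 12, and a 3+3-type rule. None of them fits all six rows. The excess over the written rule is, to within 0.001, the chance of exactly one event, which is the outcome in which the rule keeps the starting dose.

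**Second column.** The printed 0.033, 0.114, 0.345, 0.580, 0.767 and 0.890 match P(X ≥ 2) for a single cohort of six, with a largest difference of 0.0006. The two columns therefore use different thresholds, although the text states only one. To rounding, the right values for the first column are the ones printed in the second.

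**What this means for the rule.**

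- At p = 0.3 the chance of keeping the starting dose is 1 − 0.5798 = 0.420 under the rule, against 1 − 0.883 = 0.117 implied by the table.
- At p = 0.2 the same comparison is 1 − 0.3446 = 0.655 against 1 − 0.738 = 0.262.
- At p = 0.05 the chance of reducing the dose is 0.033 under the rule, against 0.265 in the table.

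**The case against.** The arithmetic on the first column is not in dispute. The arguments on the other side concern its surroundings and its weight.

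- **The table drives no decision.** The trigger is written out in both sections, and the two-stage efficacy design does not use these probabilities. Sections 5.1, 5.3.1 and 6.1 already give EGF816 at 100 mg as the standard dose, so the decision about 150 mg may be past, although section 1.1 still names 150 mg. This stands. It limits the practical weight but does not make the column right.
- **The second column cannot simply be called correct.** Section 13.7 gives no explicit stopping rule for the lower-dose cohort. If the heading is read as the overall chance of failing both cohorts, with the more-than-1-of-6 rule and the same rate at both doses, the values would be the squares of P(X ≥ 2): 0.001, 0.013, 0.119, 0.336, 0.588 and 0.793. This stands as a caution. The introductory sentence favours the conditional reading, and only under that reading and the same threshold is the second column right.
- **The event definition is not worded identically.** Section 5.1 excludes rash; section 13.7 does not repeat this but refers back to 5.1. This changes which events count towards the true rate, not the binomial threshold at a given rate.
- **How the column was produced is unknown.** Four of its six values (0.468, 0.883, 0.954, 0.985) are not exact roundings of P(X ≥ 1). Small numerical error could account for gaps below 0.001, but not for gaps of 9 to 39 points.

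**Conclusion.** The concern holds. The first probability column does not describe the rule in sections 5.1 and 13.7. It matches a trigger of at least 1 of 6, which appears nowhere in the document, and it overstates the chance of de-escalation by 9.4 points (at a 50% true rate) to 39.3 points (at 20%).

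The result assumes independent events with a common rate across the six patients, which is what a table indexed by one true toxicity rate implies. It should be corrected. The consequence is confined to how the run-in is described: the threshold is clear and consistent, and the sample size, primary endpoint and efficacy boundary are untouched. If the 150 mg stage is over, the correction mainly repairs the record of the design.

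**What to change.** Replace the first probability column with P(X ≥ 2 of 6): 0.033, 0.114, 0.345, 0.580, 0.767 and 0.891. If a single event was meant to trigger de-escalation, keep the column and change the rule in both 5.1 and 13.7 instead.

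For the second column, the sponsor should first confirm that the lower-dose cohort uses the same threshold and state that rule in 13.7. The values can then stay (0.890 becomes 0.891 if exact rounding is wanted), under a heading such as: probability of failing the lower-dose cohort, given that it is opened (more than 1 of 6).

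The cost is six numbers, one heading and one confirming sentence. The stated chance of de-escalating from a toxic dose becomes less favourable; nothing in the efficacy design changes.

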## **1. OBJECTIVES**

## 1.1 Study Design

This is a single arm, open-label phase II study evaluating the safety and efficacy of the combination of the third-generation EGFR inhibitor EGF816 with the first-generation EGFR inhibitor gefitinib in the treatment of TKI-naïve *EGFR*-mutant non-small cell lung cancer. The study will have a Simon two-stage design with eleven patients enrolled in the first stage and a plan to enroll a total of 36 patients (25 patients in the second stage) if at least seven patients remain progression-free at nine months in the first stage. The first six patients enrolled in the study will constitute a safety run-in evaluating the safety of the combination of EGF816 at the recommended phase II dose of 150mg QD and gefitinib at a standard dose of 250mg QD. If unexpected toxicities are observed among the first six patients, expansion cohorts will be added to explore different doses and/or schedules of the combination.

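### The trial-stopping probabilities in the section 13.7 run-in table hold only given de-escalation and under a lower-dose threshold that is not written down; as headed, they are too high

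*Combined protocol and SAP*

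**What the plan says.** Section 13.7 describes a run-in of up to two cohorts. The first is fixed: "The first six patients in the study will constitute a safety cohort as outlined in section 5.1". The trigger follows: "If >1 patient has a grade 3 or higher treatment-related adverse event during cycle 1 of treatment, the dose will be de-escalated as outlined". Section 5.1 gives the same count, "occurring in > 1/6 patients during the safety run-in", with rash excluded. If the trigger is met, "Six additional patients will be treated at the lower dose to establish safety prior to proceeding to open enrolment of the remainder of the trial".

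A table follows, with one column of true toxicity rates and two columns of probabilities. One is for reducing the starting dose: 0.265, 0.468, 0.738, 0.883, 0.954, 0.985. The other is for stopping the trial: 0.033, 0.114, 0.345, 0.580, 0.767, 0.890. The lead-in describes the second as "the probability of stopping the trial after the safety run in at the lower dose based on assumptions about the associated underlying toxicity rates".

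Section 13.7 therefore names stopping after the lower-dose cohort but gives no count that would cause it. Two other sections say what follows toxicity in the first six patients. Section 5.1 says that "further expansion cohorts at lower dose levels will be explored", and section 1.1 says that "expansion cohorts will be added to explore different doses and/or schedules of the combination". Neither mentions stopping the trial.

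**The concern.** The lower-dose cohort exists only if the first cohort has already triggered. A trial that stops after that cohort must have exceeded its threshold twice, so its unconditional probability is a product of two terms. The printed column contains only one term. Nothing in its header tells the reader to condition on de-escalation, and a single toxicity rate stands beside both probabilities. A reader would take the row for 0.3 to mean that 58% of such trials stop.

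This table is the only place where the documents quantify how the run-in performs, and section 13.5 lists interim monitoring as not applicable. Those judging the safety plan should be able to tell how often the rule would halt the trial, and which rule that is.

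**Working it through.** **Inputs.** Cohorts of six at each dose (13.7). Trigger at the starting dose: more than 1 of 6, that is X ≥ 2 (5.1 and 13.7). True rates and printed probabilities: the table in 13.7. The lower-dose threshold is not stated, so X ≥ 2 of 6 is an assumption there.

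**Formulas**, with n = 6 and independent patients:

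- P1(p) = P(X ≥ 1) = 1 − (1−p)^6
- P2(p) = P(X ≥ 2) = 1 − (1−p)^6 − 6p(1−p)^5

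**Step 1: reproduce the printed columns.** At p = 0.3, P1 = 1 − 0.1176 = 0.8824 (printed 0.883) and P2 = 1 − 0.1176 − 0.3025 = 0.5798 (printed 0.580, in the stopping column). All rows:

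| True rate | Printed: reduce dose | P1 | Printed: stop trial | P2 | Both cohorts trigger, P2 × P2 | Printed stop ÷ P2 × P2 |
|---|---|---|---|---|---|---|
| 0.05 | 0.265 | 0.2649 | 0.033 | 0.0328 | 0.0011 | about 31 |
| 0.1 | 0.468 | 0.4686 | 0.114 | 0.1143 | 0.0131 | 8.7 |
| 0.2 | 0.738 | 0.7379 | 0.345 | 0.3446 | 0.1188 | 2.9 |
| 0.3 | 0.883 | 0.8824 | 0.580 | 0.5798 | 0.3362 | 1.7 |
| 0.4 | 0.954 | 0.9533 | 0.767 | 0.7667 | 0.5879 | 1.3 |
| 0.5 | 0.985 | 0.9844 | 0.890 | 0.8906 | 0.7932 | 1.1 |

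The stopping column is P2 for one cohort in every row, to within 0.001. The de-escalation column is P1 in every row, although the written trigger is more than one patient. Under that trigger it would be P2: 0.033, 0.114, 0.345, 0.580, 0.767, 0.891.

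**Step 2: trial-level probability.** Let p be the rate at the starting dose and q the rate at the lower dose. Then P(stop) = P2(p) × P2(q). With p = q this is the sixth column of the table. With a less toxic second dose:

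- p = 0.3, q = 0.2: 0.5798 × 0.3446 = 0.200
- p = 0.4, q = 0.3: 0.7667 × 0.5798 = 0.445

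**Step 3: does the direction depend on the assumptions?** If the row's rate is q, the product is below P2(q) for any p below 1. If the row's rate is p and q ≤ p, the product is at most P2(p) squared, which is below P2(p). If the first trigger is taken as at least one event, as the de-escalation column was actually computed, P1 × P2 is 0.009, 0.054, 0.254, 0.512, 0.731, 0.877. That is still below the printed value in each row.

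**The case against.** The strongest defence is that the column is meant to be conditional. The lead-in places the stop after the lower-dose run-in and speaks of associated toxicity rates. This can fairly be read as the chance of stopping once that cohort has been treated, at that dose's rate. On this reading, with more than 1 in 6 as the threshold, all six values are right to within rounding. That stands, so the flat statement that the column is an arithmetic error in every row goes further than the documents allow.

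Three other inferences are tempting and should not be drawn.

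- A reader might infer that sections 1.1 and 5.1 contradict a stop by promising further cohorts. Both sentences concern toxicity in the first six patients. They are silent on excess toxicity in the lower-dose cohort and do not rule out a later stop.
- A reader might infer that, because a corrected de-escalation column would equal the stopping column, every de-escalated trial would stop. That follows only if the stopping column is already taken as unconditional. Read conditionally, equal columns are what one threshold applied to two cohorts of six produces.
- A reader might infer that patients are less protected than planned. The decision at the starting dose follows the written count, not the table, and section 12.2 has the monitoring committee reviewing toxicity up to four times a year or more often.

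It is also true that part of the gap comes from the other column's error. With the first trigger as that column was computed, the differences at rates 0.3, 0.4 and 0.5 shrink to about 0.07, 0.04 and 0.01. What survives is that the header carries no condition, the dose to which the rate applies is not named, and the threshold has to be inferred from the numbers.

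**Conclusion.** The point holds in a limited form. The stopping column is a single-cohort probability. It is valid given de-escalation, at the lower-dose rate, and under an assumed threshold of more than 1 in 6. Taken as its header reads, it is too high: at a true rate of 0.3, 0.580 is printed against 0.336 for the two-cohort sequence.

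The size rests on three assumptions: independent patients, the written trigger applied at both doses, and a common toxicity rate. The documents state the trigger for the starting dose only and do not state a common rate. A lower second rate reduces the probability further.

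The largest ratios fall at rates of 0.05 and 0.1, where a lower stopping probability is favourable because it means fewer false stops. The consequence is confined to the reported safety operating characteristics. The two-stage efficacy design and the primary analysis do not depend on this table.

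**What to change.** Make one of two changes to the stopping column:

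- relabel it as the probability given de-escalation, at the lower-dose toxicity rate; or
- replace it with P(more than 1 of 6 at the starting dose) × P(more than 1 of 6 at the lower dose), with rows for equal rates and for a lower rate at the second dose.

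Either way, state which dose each rate refers to. This also requires the dose statements to be reconciled: section 1.1 describes the run-in at 150 mg of EGF816, while section 5.1 gives 100 mg both as the de-escalated dose and as the dose for all patients.

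In the same edit, recompute the de-escalation column for the written trigger. The sponsor should reconcile sections 1.1, 5.1 and 13.7 on what follows excess toxicity in the lower-dose cohort, so that the table describes a written rule. If that rule is not more than 1 in 6, the stopping probabilities must be recomputed for it. No particular clinical rule is proposed here.

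The cost is one short table and a sentence or two of text. Sample size and the primary analysis do not change.

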#### **14. PUBLICATION PLAN**

The results should be made public within 24 months of reaching the end of the study. The end of the study is the time point at which the last data items are to be reported, or after the outcome data are sufficiently mature for analysis, as defined in the section on Sample Size, Accrual Rate and Study Duration. If a report is planned to be published in a peer-reviewed journal, then that initial release may be an abstract that meets the requirements of the International Committee of Medical Journal Editors. A full report of the outcomes should be made public no later than three (3) years after the end of the study.

		90	Able to carry on normal activity; minor signs or symptoms of disease.
1	Symptoms, but ambulatory. Restricted in physically strenuous activity, but ambulatory and able to carry out work of a light or sedentary nature ( e.g. , light housework, office work).	80	Normal activity with effort; some signs or symptoms of disease.
		70	Cares for self, unable to carry on normal activity or to do active work.
2	In bed <50% of the time. Ambulatory and capable of all self-care, but unable to carry out	60	Requires occasional assistance, but is able to care for most of his/her needs.
	any work activities. Up and about more than 50% of waking hours.	50	Requires considerable assistance and frequent medical care.
3	In bed >50% of the time. Capable of only limited self-care, confined to bed or chair more than 50% of waking hours.	40	Disabled, requires special care and assistance.
		30	Severely disabled, hospitalization indicated. Death not imminent.
4	100% bedridden. Completely disabled. Cannot carry on any self-care. Totally confined to bed or chair.	20	Very sick, hospitalization indicated. Death not imminent.
		10	Moribund, fatal processes progressing rapidly.
5	Dead.	0	Dead.

#### APPENDIX A PERFORMANCE STATUS CRITERIA

\_

#### APPENDIX B INFORMATION ON USE OF CONCOMITANT MEDICATIONS

# Table 13-1: Permitted Concomitant Medications Requiring Caution.

Mechanism of Interaction	Drug Name	
Moderate CYP3A4 inhibitor	Antibiotics: ciprofloxacin, erythromycin	
	Protease Inhibitors: amprenavir, atazanavir,	
	darunavir, fosamprenavir	
	Antifungals: fluconazole	
	Antiviral: faldaprevir	
	Calcium Channel Blockers: diltiazem, verapamil	
	Other: aprepitant, casopitant, cimetidine,	
	cyclosporine, dronedarone, lomitapide netupitant,	
	schisandra sphenanthera, tofisopam	
Moderate CYP3A4 inducer	bosentan, efavirenz, etravirine, genistein,	
	modafinil, nafcillin, [semagacestat], [talviraline],	
	thioridazine, lersivirine	
BCRP substrate	methotrexate, mitoxantrone, rosuvastatin,	
	sulfasalazine	
MATE substrate	Metformin, tenofovir	
Potent P-gp inhibitor	quinidine, dronedarone, valspodar (PSC 833),	
	elacridar (GF120918)	
Source: Adapted from Oncology Clinical Pharmacol Apr2015) which was compiled from the Indiana Univ Table and supplemented with the FDA Draft Guidar Design, Data Analysis,	versity School of Medicine's "Clinically Relevant"	
and Implications for Dosing and Labeling (February 2012), and the University of Washington's Drug Interaction Database. Please note that this list may not be exhaustive. For the latest information, please refer to the above mentioned database.		
Drugs between brackets are not marketed in US. Sensitive substrates: Drugs that exhibit an AUC ratio (AUCi/AUC) of 5-fold or more when co- administered with a known potent inhibitor. Potent P-gp inhibitor, which results in AUC ratio>2-fold.		

